7.3 LOST TO FOLLOW-UP

A subject will be considered lost to follow-up if he or she fails to return for any scheduled visit and is unable to be contacted by the study site staff.

The following actions must be taken if a subject fails to return to the clinic for a required study visit:

- The site will attempt to contact the subject and reschedule the missed visit within time window and counsel the subject on the importance of maintaining the assigned visit schedule and ascertain if the subject wishes to and/or should continue in the study.
- Before a subject is deemed lost to follow-up, the investigator or designee will make every effort to regain contact with the subject. These contact attempts should be documented in the subject's medical record or study file.
- Should the subject continue to be unreachable, he or she will be considered to have withdrawn from the study with a primary reason of lost to follow-up.

8 STUDY ASSESSMENTS AND PROCEDURES

8.1 EFFICACY ASSESSMENTS

The baseline value of each assessment will be the value assessed closest and prior to the first dose of TWB-103.

8.1.1 ULCER EVALUATION-WOUND SIZE

The surface area of the ulcer will be estimated in the manner as follows. The ulcer along with an ulcer measuring ruler (OPSITE™ transparent film) will be photographed. An OPSITE™ transparent film will be placed on the wound and the wound area is traced on the film. The images will be processed and analyzed using the ImageJ software package (National Institutes of Health, <http://rsb.info.nih.gov/ij/download.html>). The ImageJ software read the computed tomographic data and calibrated the images automatically.

Wound closure was defined as “full epithelialization of the wound with the absence of drainage or dressing requirement and without sign of abscess under the epithelium”. An ulcer was considered healed only after closure was re-confirmed at the visit 2 weeks later. Therefore, a wound closure should be observed at three consecutive visits (i.e. a duration of 2 weeks) for an ulcer to be deemed as healed. For example, when the wound closure is first observed at Week 8 and subsequently at Week 9 and Week 10, the ulcer is “healed”. If the subject misses Week 9 or Week 10 visits or wound closure is not present at Weeks 9 and 10, this ulcer is not defined as “healed on week 8”.

8.1.2 ULCER EVALUATION-WOUND GRADING

The grading of ulcer will be performed at screening only as part of the eligibility check according to the Wagner Grading System⁷, which is described below:

Grade 1: Superficial diabetic ulcer

Grade 2: Ulcer extension

1. Involves ligament, tendon, joint capsule or fascia
2. No abscess or osteomyelitis

Grade 3: Deep ulcer with abscess or osteomyelitis

Grade 4: Gangrene to portion of forefoot

Grade 5: Extensive gangrene of foot

8.1.3 ULCER EVALUATION-WOUND VOLUME (OPTIONAL)

The wound volume may be measured by using 3D camera and analysis software, which will be provided by the sponsor.

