Objectives: **Primary Objective:** To assess the safety profile of TWB-103 administered to subjects with diabetic lower limb ulcers

Secondary Objective: To explore the efficacy of TWB-103 administered to subjects with diabetic lower limb ulcers

Endpoints: **Primary Endpoint:** Incidence of adverse events (AEs) and serious adverse events (SAEs). Pre-existing abnormalities are considered as AE or SAE only when the conditions escalate. The following events should be discussed

specifically:

1. Study wound and its periphery: Infection, pain, pruritus/irritation, skin dysfunction/blister, osteomyelitis, cellulitis, edema/swelling and unexpected surgery
2. Non-study area and systemic: Infection, pain, pruritus/irritation, skin dysfunction/blister, osteomyelitis, cellulitis, edema/swelling, unexpected surgery, accidental injury, abnormal lab test and general disorders

Secondary Endpoints:

1. The percentage of subjects with confirmed study wound closure at each week up to 12 weeks.
* Wound closure is defined as “full epithelialization of the wound with the absence of drainage or dressing requirement and without sign of abscess under the epithelium”. An ulcer is considered healed only after wound closure is re-confirmed at the visit 2 weeks later. Therefore, a wound closure should be observed at three consecutive visits (i.e. a duration of 2 weeks) for an ulcer to be deemed as healed.
2. Time (days) to confirmed wound closure for those subjects whose wounds are healed during treatment period and during the study period.
3. Reduction of individual wound area for up to 12 weeks.
4. Reduction of wound area at each week up to 12 weeks.
5. General granulation rate and quality of granulation tissue.
6. Reduction of wound volume for individual subject measured by 3D camera and analysis software up to 12 weeks (only for those subjects who have received the 3D measurement).

Study Population:

Ten subjects aged at least 20 years old (inclusive) with diabetic lower limb ulcers presented for at least 4 weeks are planned to enroll in Taiwan.

Inclusion Criteria

In order to be eligible to participate in this study, an individual must meet all of the following criteria:

1. Adults at least 20 years of age.

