4. If the withdrawal is decided during TWB-103 treatment period, the withdrawn subject will be encouraged to complete the assessments of Week 12, within 1 week of the withdrawal decision, as End of Study (EOS) visit, before exiting from the study. Laboratory, pregnancy and PRA tests done within 1 week prior to EOS visit are acceptable.
5. If the withdrawal is decided during the follow-up period, the withdrawn subject will be encouraged to complete the assessments of Week 36, within 2 weeks of the withdrawal decision, as EOS visit, before exiting from the study.
6. Unscheduled visit will be arranged when investigator considers necessary. Actions (pregnancy test, laboratory test, PRA test, ulcer evaluation, standard of care) to be performed will be per investigator's decision.
7. Eligibility will be checked during screening and at Day 1 Visit. The eligibility re-check at Day 1 will be based on the results from Day 1 Visit (vital signs and physical exam) and other information collected during screening.
8. Procedures to be performed before TWB-103 application. If debridement is performed as part of the standard of care, debridement should be performed before TWB-103 application.
9. The baseline value of each assessment will be the value assessed closest and prior to the first dose of TWB-103.
10. Pregnancy test and laboratory test will be performed at Week 5 Visit only. Pregnancy test and laboratory test performed within 1 week prior to Week 5 Visit will be acceptable.
11. Laboratory, pregnancy and PRA tests done within 1 week prior to Week 12 or End-of-Treatment visit are acceptable.
12. Standard of care will be performed at the investigator's discretion.
13. Ulcer evaluation includes wound size, wound volume (optional), granulation rate and quality of granulation tissue, and grading. The wound grading will be performed at screening only. The ulcer evaluation before and after the standard-of-care treatment should be recorded during screening period (also see footnote 2).
14. Revascularization is prohibited during treatment period (Visit 2~Visit 13).

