6.1.2 DOSING AND ADMINISTRATION

Dosing

Each subject will receive TWB-103 weekly up to 12 applications or till confirmed wound closure, whichever comes first. TWB-103 is applied to the ulcer at appropriate amount based on the ulcer area. The dosage of TWB-103 used in this study is 0.15 ml TWB-103/cm² of ulcer area. Detailed protocol of preparing TWB-103 for clinical application will be provided by study sponsor.

Before Administration

- (1) Before TWB-103 Treatment starts, the wound dressing and topical drugs used during screen period should be removed first. Attention should be paid to viscous substances such as gel or ointment and anti-microbial substances because they may interfere with the subsequent TWB-103 treatment by conferring physical barrier or cytotoxicity to cells in TWB-103. If such substance has been applied previously, the substance should be thoroughly washed off by flushing with sterile saline or wiping off with saline-saturated cotton swabs.
- (2) Wound debridement may be performed based on Investigator's judgment. Epinephrine is allowed for reducing bleed.
- (3) When bleeding stops, an OPSITE™ transparent film is placed on the wound and the wound area is traced on the film. The area of the wound is estimated using the grid pattern on the film. The investigator is allowed to perform additional wound measurement with a 3D camera combined with software which is capable of estimation of wound dimensions.

(4) Surgical removal of excessive granulation tissue and minor wound debridement are allowed during study period. However, such events should be recorded and photo images before and after the procedure should be taken.

Administration

- (1) TWB-103 is pushed from the syringe to the wound. The wound is then covered by Tegaderm™ transparent film. If the wound is positioned in a way that TWB-103 might flow-off easily, a collagen wound dressing (provided by Sponsor) can be placed within the wound after TWB-103 administration and before covering the wound with the Tegaderm™ transparent film. It is appropriate that the collagen dressing loosely fills the wound after it is applied. Prewetting of the collagen dressing is not suggested since TWB-103 contains sufficient liquid.
- (2) Then, gauze pad, additional dressings, fixation bandages or sleeves, etc. may be applied over the wound for further protection.
- (3) Gauze pad and dressing on top of Tegaderm™ transparent film should be replaced as frequently as needed for good wound care.

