6.3 MEASURES TO MINIMIZE BIAS: RANDOMIZATION AND BLINDING

As this is an open-label study, no blinding will be used in this study.

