9.4 STATISTICAL ANALYSES

9.4.1 GENERAL APPROACH

There will be a separate formal statistical analysis plan (SAP) to be completed prior to database/data lock. The SAP generally includes additional statistical analysis detail (e.g., more detail of analysis populations, summary of statistical strategies). Any deviations from the planned analysis as described in the SAP will be justified and recorded in the final clinical study report.

The baseline value of each assessment will be the value assessed closest and prior to 1st application of TWB-103.

Descriptive statistics will be provided for all endpoints.

Continuous variables will be summarized by reporting the number of observations, mean, standard deviation, median, interquartile range (IQR = third quartile (Q3) - first quartile (Q1)), Q1, Q3, minimum and maximum.

Categorical variables will be summarized using frequency tables showing the number and percentage of subjects within a particular category.

Ordinal endpoints will be presented by transition tables.

Healing time from baseline to wound closure will be estimated by using Kaplan-Meier method.

The data changes from baseline value will be analyzed by one-sample t-test or Wilcoxon sign rank test. The baseline value of each assessment will be the value assessed closest and prior to 1st application of TWB-103. The Last Observation Carried Forward (LOCF) method will be applied for dealing missing data of the efficacy endpoints.

All comparisons will be conducted with significance level of 0.05, using 2-tailed tests where 95% confidence interval for difference and corresponding *p*-value will be presented.

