9.4.3 ANALYSIS OF THE SECONDARY ENDPOINTS

For changes of wound area and (if data available) wound volume measured by 3D camera from the baseline values, data will be analyzed by using one-sample t-test or Wilcoxon sign rank test on ITT and PP population.

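### Wound volume is optional at every visit, yet its change is tested at 0.05 under a general LOCF rule that does not exempt it

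*Combined protocol and SAP*

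**What the plan says.** **Measurement.** Section 8.1.3 states: "The wound volume may be measured by using 3D camera and analysis software, which will be provided by the sponsor". Section 6.1.2, Before Administration item (3), leaves the decision with the investigator: "The investigator is allowed to perform additional wound measurement with a 3D camera combined with software which is capable of estimation of wound dimensions". A footnote to the Schedule of Activities (Section 1.3) reads "Ulcer evaluation includes wound size, wound volume (optional), granulation rate and quality of granulation tissue, and grading", and the visit lists in Sections 8.3.1 to 8.3.5 repeat the optional label from screening through follow-up. No section says which subjects or visits are to be measured, or requires a volume before the first dose.

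**Blinding.** Section 6.3: "As this is an open-label study, no blinding will be used in this study".

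**Endpoint.** The Synopsis and Section 3 list volume reduction up to Week 12 as the sixth of six secondary endpoints, "only for those subjects who have received the 3D measurement".

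**Analysis.** Section 9.4.3 analyses the change in volume from baseline, if there are data, by one-sample t-test or Wilcoxon signed-rank test in ITT and PP. Section 9.4.1 sets two-sided 0.05 for all comparisons, with confidence interval and p-value, and adds: "The Last Observation Carried Forward (LOCF) method will be applied for dealing missing data of the efficacy endpoints". Volume is not exempted. Sections 8.1 and 9.4.1 define baseline as the last value before the first application.

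**Context.** Section 9.1 has no hypotheses, Section 9.2 plans 10 subjects for 8 evaluable, and Section 9.3 rests the main conclusion on the primary endpoint, which is safety.

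**The concern.** A missing-data rule presupposes a schedule against which a value can be missing. Volume has none. Applied literally, the LOCF sentence fills every visit at which the investigator did not use the camera, including visits where no one meant to use it, and the filled series is then tested as if it were a Week 12 result.

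The person deciding whether to measure also sees the wound and knows the treatment. Which subjects have post-baseline volumes, and at which visits, may therefore depend on how the wound looks. The planned test cannot reveal such dependence.

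At stake is the only quantitative post-baseline measure that reflects depth. Eligible wounds are full-thickness and may extend to tendon or joint capsule (Section 5.1, criterion 7), whereas area is a two-dimensional tracing (Section 8.1.1), Wagner grade is recorded at screening only (Section 8.1.2) and granulation is recorded as comments (Section 8.1.4).

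**Working it through.** **1. Is there a figure to reproduce?** No. The protocol gives no expected number of subjects or visits with a volume, and no SD, effect size or power. The only count is 10 enrolled for 8 evaluable.

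**2. Who enters the analysis?** Change at week *w* is V(w) − V(0), where V(0) is the last pre-dose volume. Without V(0) the change is undefined and the subject drops out, and LOCF cannot repair that. Entry therefore requires a measurement made before any response to TWB-103 can be seen. Selection on on-treatment appearance can act only through the later measurements.

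**3. What can LOCF do?** There are 12 weekly post-baseline evaluations (Weeks 1 to 12). A subject measured before dosing and at Week 1 only would, read literally, have 12 − 1 = 11 carried values, Week 12 among them. If the last measured week is *k*, the analysed reduction is V(0) − V(k) instead of V(0) − V(12), so the error is V(12) − V(k):
- wound still shrinking after *k*: V(12) < V(k), and the reduction is understated;
- wound enlarging after *k*: V(12) > V(k), and the reduction is overstated.

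The direction is not fixed by the plan.

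**4. How much could appearance-driven measurement matter?** This is an illustration only; every input except the 10 subjects and 12 weekly visits is an assumption. All 10 subjects have a baseline, there is no true change, visit-to-visit correlation is 0.8, the Week 12 value is taken by LOCF, the test is a t-test, and there are 4,000 runs per setting. The chance of measurement rises with a better-looking wound by 0, 0.5 or 1.0 log-odds per SD. Cells show the rejection rate at nominal 5%, with the bias towards improvement in SD of change.

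| Visits measured (about) | Week 12 values carried | No dependence | 0.5 per SD | 1.0 per SD |
|---|---|---|---|---|
| 20% | 74–78% | 4.5% (0.00) | 9.6% (0.21) | 22% (0.39) |
| 50% | 50% | 5.3% (0.00) | 5.5% (0.08) | 8.5% (0.18) |
| 80% | 20–24% | 5.3% (0.00) | 4.8% (0.03) | 5.9% (0.05) |

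The Monte Carlo standard error near 5% is √(0.05 × 0.95 / 4000) = 0.34 percentage points. With every visit measured, the test rejects in about 5% of runs. If worse-looking wounds were preferred instead, symmetry gives the same rejection rates with the bias reversed. The illustration has no healing trend, so it leaves out the effect in step 3.

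**5. What can the test show in a small subset?** The smallest two-sided exact signed-rank p is 2/2ⁿ: 2/32 = 0.0625 at n = 5 and 2/64 = 0.031 at n = 6. The 0.0625 floor belongs to the signed-rank test with 5 subjects. The t-test, which Section 9.4.3 also allows, has no such floor. Its standardised change detectable with 80% power is 1.69 SD at n = 5, 1.16 at n = 8 and 1.00 at n = 10.

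**The case against.** The case on the other side is substantial.

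- *The restriction is declared.* Endpoint 6 is openly limited to measured subjects and Section 9.4.3 is conditional on data. This stands: the analysed set is the measured part of ITT and PP, and that is not in itself an error. What is absent is the rule that creates the subset.
- *LOCF may not apply.* The text does not say that an optional measurement not taken counts as missing, and Section 9.4.1 leaves further detail to a separate SAP. This stands in part: LOCF may fill those visits, and it is not certain that it will. But that SAP need only be complete before data lock in an open-label trial, and it cannot recover a pre-dose volume that was never taken.
- *A reader might infer that subjects are hand-picked for good response and that the reduction is inflated.* The documents do not support this. The baseline rule blocks selection at entry on treatment response, nothing shows that measurement will follow appearance, an investigator might equally prefer deep or stalled wounds, and LOCF in a shrinking wound understates the reduction.
- *A reader might infer that a small subset can never reach 0.05.* That fails for the permitted t-test.
- *Little depends on it.* This stands and sets the weight of the point: volume is the last of six endpoints under an exploratory objective, and area is not optional.

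**Conclusion.** The point holds as a minor one. A measurement with no set schedule, taken at the discretion of an unblinded investigator, is given a significance test and a general LOCF rule that does not exempt it. Following the plan as written can put an early volume in place of Week 12, and availability of post-baseline values may depend on the look of the wound. Subjects without a pre-dose volume fall out of the change analysis.

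Neither the direction nor the size of any bias can be derived from the documents. The simulated rates show only that the test keeps its level when measurement is unrelated to appearance or is nearly complete, and can lose it when measurement is sparse and appearance-driven. They are not estimates for this trial. The safety conclusion and the wound-area results are untouched.

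**What to change.** **Sections 8.1.3 and 6.1.2, Before Administration item (3):** decide before the first application whether a subject belongs to the volume set, for example by camera availability at the site. For those subjects, take a volume before the first dose and at pre-specified visits up to Week 12.

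**Sections 9.4.1 and 9.4.3:** exempt volume from LOCF. Report observed individual values and descriptive summaries with the number measured at each visit, and no p-value. Individual values also suit endpoint 6, which is already framed per subject.

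**Cost:** one exploratory p-value is lost, and some additional measurements are needed where the camera is already in use. The documents do not say which sites will have the camera, so the number of extra measurements cannot be stated.

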8.1.4 ULCER EVALUATION-GRANULATION RATE AND QUALITY OF GRANULATION TISSUE

Granulation rate and quality of granulation tissue will be recorded by comments from the investigator.

Healthy granulation tissue is pink to red, moist, and shiny. Forming of healthy granulation tissue provides foundation for epithelialization and is an indicator of healing. Stalled granulation process often associates with prolonged inflammation, lack of vascularization, infection or other abnormalities. Hypergranulation may occur during wound healing, which may deter epithelialization. Should it occur, the excessive tissue may be trimmed off surgically before administration of TWB-103. Images before and after excision should be recorded.

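### Secondary endpoint 5 (granulation) is recorded only as investigator comments, so the descriptive summaries promised for all endpoints cannot be produced from the data as specified

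*Combined protocol and SAP*

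**What the plan says.** The Synopsis (1.1) and the table in section 3 of the protocol list "General granulation rate and quality of granulation tissue" as secondary endpoint 5. Neither attaches a unit, scale or time point to it.

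Section 8.1.4 gives the only recording method: "Granulation rate and quality of granulation tissue will be recorded by comments from the investigator". It then describes tissue in prose, for example "Healthy granulation tissue is pink to red, moist, and shiny", and mentions stalled granulation and hypergranulation. It does not turn these descriptions into levels to be recorded. Footnote 13 of the Schedule of Activities and sections 8.3.1 to 8.3.5 include granulation in the ulcer evaluation at every scheduled visit, from screening to the end of follow-up.

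On analysis, section 9.4.1 sets general rules:
- As a rule covering everything: "Descriptive statistics will be provided for all endpoints"
- On data that fall into classes: "Categorical variables will be summarized using frequency tables showing the number and percentage of subjects within a particular category"
- On data with ordered levels: "Ordinal endpoints will be presented by transition tables"
- On gaps in the efficacy data: "The Last Observation Carried Forward (LOCF) method will be applied for dealing missing data of the efficacy endpoints"

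Section 9.4.3, on the secondary endpoints, names only wound area and wound volume. Section 8.1.2 says of the Wagner grade that "The grading of ulcer will be performed at screening only as part of the eligibility check".

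**The concern.** The protocol commits to summarising an endpoint for which it defines no variable. If 8.1.4 is followed literally, the analyst receives a set of comments and has two choices: list them, which is not what 9.4.1 promises, or devise categories and code the comments once the visits are over. The study is open-label (6.3) and runs at several sites (Synopsis). Investigators may therefore comment on different attributes at different visits, and whoever codes the comments may already know which ulcers closed.

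What is at stake is one of six secondary endpoints. Section 3 justifies the efficacy endpoints partly by the appearance of the wound bed, and 8.1.4 treats healthy granulation as a sign of healing. The sponsor evidently wants usable information from this endpoint.

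**Working it through.** This is mainly a comparison of sections; the only arithmetic is a visit count. The plan gives no figure of its own to reproduce.

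**Step 1. What each rule in 9.4.1 needs, against what 8.1.4 supplies.**
- Mean, SD, median and quartiles need a number. 8.1.4 supplies none, and the word rate has no numerator, denominator or time reference.
- Frequency tables need predefined categories. 8.1.4 describes kinds of tissue but sets no categories and does not require each visit to be assigned to one.
- Transition tables need ordered levels at baseline and at a later visit. No ordered levels are given.
- LOCF needs a value to carry forward. Carrying a narrative comment to a later visit has no clear meaning.

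None of the four can be carried out on the data as specified, and 9.4.3 does not fill the gap.

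**Step 2. Which secondary endpoint the transition tables could serve.**
- Endpoint 1 (confirmed closure by week) is binary.
- Endpoint 2 (time to confirmed closure) is time-to-event.
- Endpoints 3, 4 and 6 (area, area by week, volume) are continuous.
- Endpoint 5 (granulation) is of no stated type.

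The Wagner grade is ordinal, but it is taken once and is not a listed endpoint, so it cannot show a transition. By elimination, granulation is the only secondary endpoint that could be ordinal. That is an inference; no section says so.

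**Step 3. How many evaluations are involved.** Inputs: visit numbers from the Schedule of Activities and 10 planned subjects (9.2).
- Visits 1 to 14 (screening through Week 12): 14 per subject.
- Visits 15 to 21 (follow-up): 7 per subject, so 14 + 7 = 21 in all.
- For 10 subjects the ceilings are 14 × 10 = 140 and 21 × 10 = 210.

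This counts visits. Screening calls for an evaluation before and after standard of care, but the second may coincide with Day 1. Early confirmed closure removes treatment visits, withdrawal removes more, and a closed ulcer has no granulating bed to rate. The totals are therefore upper limits on the evaluations, not a count of lost values.

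**Step 4. What could be recovered later.** Section 8.1.1 has the ulcer photographed as part of the area measurement, and 8.1.4 calls for images before and after excess tissue is removed. Colour and coverage could be read from such images, but moisture and shine less reliably. No reading of the photographs for granulation is planned.

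**The case against.** The strongest reply is that the missing definitions may exist elsewhere. Section 9.4.1 announces a separate, more detailed SAP, and neither that SAP nor the CRF is among the documents reviewed. The word comments does not prove that the CRF field is free text. This stands as a limit: the conclusion applies to the protocol as written. It does not remove the point. The SAP is due only before data lock, possibly after the last visit, and cannot then make investigators record the same attributes at each visit. If the CRF already holds structured fields, 8.1.4 is wrong about the recording method and needs correcting anyway.

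A second reply is scale. This is a 10-subject, single-arm pilot with no hypotheses (9.1) and an exploratory efficacy objective, and its main conclusion rests on the primary endpoint (9.3). A narrative account of tissue quality backed by photographs is defensible here. That stands too, and it is why a narrative listing is an acceptable fallback, provided the plan says so.

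Three stronger readings are tempting, and the documents do not support them:
- A reader might infer that transition tables are expressly planned for granulation. The sentence in 9.4.1 is a general rule by variable type and names no endpoint.
- A reader might infer that the information is lost for good once visits have passed. The photographs allow some later rating, and a reader masked to visit and outcome could do it, so biased coding is a risk and not a certainty.
- A reader might take 140 to 210 as the number of granulation values lost. Step 3 shows that these are ceilings that include closed wounds.

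**Conclusion.** The point holds. Sections 8.1.4 and 9.4.1 cannot both stand as written for endpoint 5: the recording method yields no analysable variable, and the analysis section promises summaries and imputation of one. The size is one of six secondary endpoints, at up to 14 scheduled visits per subject through Week 12 and 21 in all.

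The consequence is moderate. Neither the primary safety endpoint nor the closure, time-to-closure, area and volume endpoints depend on granulation data, so the gap gives no ground for doubting them. It is worth correcting because the remedy is cheap and works fully only if it is in place before the visits occur.

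The conclusion assumes that comments means unstructured text and that no coding scheme exists in the SAP or CRF. If one does, the correction shrinks to aligning 8.1.4 with it.

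**What to change.** In 8.1.4 and on the CRF, add two fixed fields at each scheduled ulcer evaluation and keep the comments as a supplement.

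1. **Extent.** Share of the wound bed covered by healthy granulation: 0, 1-25, 26-50, 51-75 or 76-100%, plus a separate level for a closed, fully epithelialized wound. Without that level, a healed ulcer and one with no healthy granulation would both score 0. Define granulation rate as the change in this share from baseline. The bands are a reasonable suggestion, not the only valid choice.
2. **Appearance.** Nominal categories: healthy (as 8.1.4 already describes it), not healthy, hypergranulation, and not applicable because closed. These have no natural order and should not be analysed as ordinal.

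Summarise field 1 by baseline-to-visit transition tables through Week 12 and field 2 by frequency tables, and add both to 9.4.3.

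If the fields are not adopted, state that endpoint 5 will be listed narratively only, and exempt it from the summaries and LOCF in 9.4.1.

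The cost is two CRF fields and a short site instruction, with no extra visit, staff or procedure. The rating remains subjective and is made by an unblinded investigator, so the change improves consistency but does not remove the risk of bias.
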